20.0 Potential Benefits to Subjects

20.1 Describe the potential benefits that individual subjects may experience by taking part in the research. Include the probability, magnitude, and duration of the potential benefits. Indicate if there is no direct benefit.

NOTE: Compensation cannot be stated as a benefit.

Response:

The benefits to participants may include reduced caregiver burden and depression, increased positive aspects of caregiving and self-esteem to be an effective caregiver.

21.0 Compensation for Research-Related Injury

N/A: The research procedures for this study do not present risk of research related injury (e.g. survey studies, records review studies). This section does not apply.

21.1 *If the research procedures carry a risk of research related injury, describe the available compensation to subjects in the event that such injury should occur.*

Response:

There will be no compensation for research related injury.

21.2 *Provide a copy of contract language, if any, relevant to compensation for research related injury.*

*NOTE: If the contract is not yet approved at the time of this submission, submit the current version here. If the contract is later approved with **different language regarding research related injury**, you must modify your response here and submit an amendment to the IRB for review and approval.*

Response:

It is stated in the consent form. "If you injure while caring for your care recipient, we are not responsible and compensate for the injury."

All OTGS has malpractice insurance as a mandate.

Economic Burden to Subjects

21.3 *Describe any costs that subjects may be responsible for because of participation in the research.*

NOTE: Some examples include transportation or parking.

Response:

There will be no cost for participating in this study.

N/A: This study is not enrolling subjects, or is limited to records review procedures only. This section does not apply.

22.0 *Compensation for Participation*

25.1 *Describe the amount and timing of any compensation to subjects, including monetary, course credit, or gift card compensation.*

Response:

Participants will be paid \$20 right after each interview.

N/A: This study is not enrolling subjects, or is limited to records review procedures only. This section does not apply.

N/A: There is no compensation for participation. This section does not apply.

23.0 Consent Process

23.1 Indicate whether you will be obtaining consent.

NOTE: This does not refer to consent documentation, but rather whether you will be obtaining permission from subjects to participate in a research study. Consent documentation is addressed in Section 27.0.

Yes (If yes, Provide responses to each question in this Section)
 No (If no, Skip to Section 27.0)

23.2 Describe where the consent process will take place. Include steps to maximize subjects' privacy.

Response:

The consent process will take place either caregiver (participant)'s home or the care recipient home; therefore, the participant has a total control to secure his/her privacy.

23.3 Describe how you will ensure that subjects are provided with a sufficient period of time to consider taking part in the research study.

NOTE: It is always a requirement that a prospective subject is given sufficient time to have their questions answered and consider their participation. See "SOP: Informed Consent Process for Research (HRP-090)" Sections 5.5 and 5.6.

Response:

We will provide three opportunities for individuals to decide their participation in the study. First through an invitation letter, the second is the PI's initial phone call, and the third is a face-to-face conversation with an OTGS. At the last step, the consent form will be provided and they will be asked to read each section and have questions. All OTGS will have been trained to answer questions. During this consenting process, we will give sufficient time for participants to understand the study and ask questions. After they understood the study, they will be asked to sign the consent form.

23.4 Describe any process to ensure ongoing consent, defined as a subject's willingness to continue participation for the duration of the research study.

Response:

After obtaining written consent for the initial interview, in the beginning of 2nd and 3rd interview, participants will be asked their willingness to be in the study or not. In addition, this study will involve phone contacts with participants to find whether solutions are working and make a next appointment. At that time, if we suspect unwillingness to continue to be in the study, we will ask their wish to withdraw from the study. This will be followed by the PI's contact with them for confirmation.

23.5 Indicate whether you will be following “SOP: Informed Consent Process for Research (HRP-090).” If not, or if there are any exceptions or additional details to what is covered in the SOP, describe:

- The role of the individuals listed in the application who are involved in the consent process
- The time that will be devoted to the consent discussion
- Steps that will be taken to minimize the possibility of coercion or undue influence
- Steps that will be taken to ensure the subjects’ understanding

Response:

We have reviewed and will be following “SOP: Informed Consent Process for Research (HRP-090).”

Non-English Speaking Subjects

N/A: This study will not enroll Non-English speaking subjects.
(Skip to Section 26.8)

23.6 Indicate which language(s) other than English are likely to be spoken/understood by your prospective study population or their legally authorized representatives.

NOTE: The response to this Section should correspond with your response to Section 6.4 of this protocol.

Response:

23.7 If subjects who do not speak English will be enrolled, describe the process to ensure that the oral and written information provided to those subjects will be in that language. Indicate the language that will be used by those obtaining consent.

NOTE: Guidance is provided on “SOP: Informed Consent Process for Research (HRP-090).”

Response:

Cognitively Impaired Adults

N/A: This study will not enroll cognitively impaired adults.
(Skip to Section 26.9)

23.8 *Describe the process to determine whether an individual is capable of consent.*

Response:

Adults Unable to Consent

N/A: This study will not enroll adults unable to consent.
(Skip to Section 26.13)

When a person is not capable of consent due to cognitive impairment, a legally authorized representative should be used to provide consent (Sections 26.9 and 26.10) and, where possible, assent of the individual should also be solicited (Sections 26.11 and 26.12).

23.9 *Describe how you will identify a Legally Authorized Representative (LAR). Indicate that you have reviewed the “SOP: Legally Authorized Representatives, Children, and Guardians (HRP-013)” for research in New York State.*

NOTE: Examples of acceptable response includes: verifying the electronic medical record to determine if an LAR is recorded.

Response:

We have reviewed and will be following “SOP: Legally Authorized Representatives, Children, and Guardians (HRP-013).”

23.10 *For research conducted outside of New York State, provide information that describes which individuals are authorized under applicable law to consent on behalf of a prospective subject to their participation in the research. One method of obtaining this information is to have a legal counsel or authority review your protocol along with the definition of “legally authorized representative” in “SOP: Legally Authorized Representatives, Children, and Guardians (HRP-013).”*

Response:

23.11 *Describe the process for assent of the adults:*

- *Indicate whether assent will be obtained from all, some, or none of the subjects. If some, indicate which adults will be required to assent and which will not.*

Response:

- *If assent will not be obtained from some or all subjects, provide an explanation of why not.*

Response:

23.12 *Describe whether **assent of the adult** subjects will be documented and the process to document assent.*

NOTE: The IRB allows the person obtaining assent to document assent on the consent document using the “Template Consent Document (HRP-502)” Signature Block for Assent of Adults who are Legally Unable to Consent.

Response:

Subjects who are not yet Adults (Infants, Children, and Teenagers)

N/A: This study will not enroll subjects who are not yet adults.
(Skip to Section 27.0)

23.13 *Describe the criteria that will be used to determine **whether a prospective subject has not attained the legal age for consent to treatments or procedures involved in the research** under the applicable law of the jurisdiction in which the research will be conducted (e.g., **individuals under the age of 18 years**). For research conducted in NYS, review “SOP: Legally Authorized Representatives, Children, and Guardians (HRP-013)” to be aware of which individuals in the state meet the definition of “children.”*

NOTE: Examples of acceptable responses include: verification via electronic medical record, driver’s license or state-issued ID, screening questionnaire.

Response:

23.14 *For research conducted outside of New York State, provide information that describes which persons have not attained the legal age for consent to treatments or procedures involved the research, under the applicable law of the jurisdiction in which research will be conducted. One method of obtaining this information is to have a legal counsel or authority review your protocol along the definition of “children” in “SOP: Legally Authorized Representatives, Children, and Guardians (HRP-013).”*

Response:

23.15 *Describe whether parental permission will be obtained from:*

Response:

- One parent even if the other parent is alive, known, competent, reasonably available, and shares legal responsibility for the care and custody of the child.
- Both parents unless one parent is deceased, unknown, incompetent, or not reasonably available, or when only one parent has legal responsibility for the care and custody of the child.
- Parent permission will not be obtained. A waiver of parent permission is being requested.

NOTE: The requirement for parent permission is a protocol-specific determination made by the IRB based on the risk level of the research. For guidance, review the "CHECKLIST: Children (HRP-416)."

23.16 *Describe whether permission will be obtained from individuals **other than parents**, and if so, who will be allowed to provide permission. Describe your procedure for determining an individual's authority to consent to the child's general medical care.*

Response:

23.17 *Indicate whether assent will be obtained from all, some, or none of the children. If assent will be obtained from some children, indicate which children will be required to assent.*

Response:

23.18 *When assent of children is obtained, describe how it will be documented.*

Response:

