3.0 Study Design

3.1 Describe and explain the study design (e.g. case-control, cross-sectional, ethnographic, experimental, interventional, longitudinal, observational).

Response:

We will use a qualitative method to understand difficulties that caregivers are facing and to document solutions and their implementation process; and a quantitative method using a randomized contoured trial with pre-, post- and follow-up experimental design. A treatment group will receive a 1 to 2-month interventions to solve caregiving challenges, and a control group will receive usual support. Assessments will be conducted at baseline, 2 months (posttest), 4 months (follow-up), and 6 months post intervention.

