16.0 Data Management and Analysis

16.1 *Describe the data analysis plan, including any statistical procedures. This section applies to both quantitative and qualitative analysis.*

Response:

For two hypotheses, we first analyze a linear trend of dependent variables over time. If they are linear, we will use Generalized Estimating Equation to compare the two groups' slopes. A main effect and an interaction effect will be examined. If it is not, we will use Repeated Measures ANOVA with a between-factor. The contrasts within a group and the difference between groups will be performed as post hoc tests. To answer the last research question to find the difference between

the 4-months data and 6 month after intervention (or at 10 months), we will use Repaeated measurs ANVA with a between-factor.

To answer research questions, we will list all challenges for both groups and solutions for the treatment group. The effectiveness of solutions will be evaluated using a Likert Scale (from very effective to not effective at all) and percentages will be reported. For the rate of continued community, living at 4 months will be tabulated for both groups and a chi-square test will be used. The number of falls and emergency visits will be compared for these two groups using Mann Whitney U-test.

The significance level for primary analyses will be set at .05. SPSS 26.0 will be used for statistical analyses.

16.2 If applicable, provide a power analysis.

NOTE: This may not apply to certain types of studies, including chart/records reviews, survey studies, or observational studies. This question is asked to elicit whether the investigator has an adequate sample size to achieve the study objectives and justify a conclusion.

Response:

The sample size for this study was determined by a power analysis based on the study similar to our study (Kamiya et al., 2014). The effect size found in the article was $d = .65$. We will use a directional hypothesis; therefore, we set $\alpha = .05$, and in order to achieve 80% of statistical power, we will need 30 participants in each group, therefore 60 in total. Expecting 25% of attrition, we will recruit 75 participants.

16.3 Describe any procedures that will be used for quality control of collected data.

Response:

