18.0 Withdrawal of Subjects

 N/A: This study is not enrolling subjects. This section does not apply.

18.1 Describe anticipated circumstances under which subjects may be withdrawn from the research without their consent.

Response:

We will not withdraw a participant from the research without their consent.

18.2 Describe any procedures for orderly termination.

NOTE: Examples may include return of study drug, exit interview with clinician. Include whether additional follow up is recommended for safety reasons for physical or emotional health.

Response:

If a participant decide to withdraw for the study, he/she will indicate it to an OTGS at the interview and the PI will confirm the wish through a phone contact with the participant.

18.3 Describe procedures that will be followed when subjects withdraw from the research, including retention of already collected data, and partial withdrawal from procedures with continued data collection, as applicable.

Response:

After the orderly termination, the data that had been collected until the withdrawal will be retained and analyzed. This information is included in the informed consent.

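### Sections 23.4 and 18.2–18.3 do not separate stopping the intervention from leaving the study, so outcome data may be lost differently in the two arms

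*Combined protocol and SAP*

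**What the plan says.** Section 23.4 (Consent Process) describes two checks on continuing consent. The first is a question about willingness at the start of the second and third interviews, with no restriction by arm. The second belongs to phone calls: "this study will involve phone contacts with participants to find whether solutions are working and make a next appointment". It continues: "At that time, if we suspect unwillingness to continue to be in the study, we will ask their wish to withdraw from the study". The step after that is: "This will be followed by the PI's contact with them for confirmation".

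Section 18.2 likewise has the principal investigator confirm by phone a participant's wish to withdraw. Section 18.3 says that "the data that had been collected until the withdrawal will be retained and analyzed". The template prompt above that response also asks about partial withdrawal with data collection continuing, and the response does not take this up.

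On the arms, section 3.0 says that "a control group will receive usual support", and section 16.1 plans that "we will list all challenges for both groups and solutions for the treatment group". Section 9.1 gives four to six home visits, varying by case, and makes the last assessment a phone call. Section 16.1 names Generalized Estimating Equations or repeated measures ANOVA. It gives no missing-data method, no analysis set and no comparison of attrition by arm.

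**The concern.** A caregiver may tire of the visits or solutions and still be willing to answer a 30–45 minute interview. The plan has no route for that person. If staff sense reluctance on a call, the question they ask is about leaving the study, and the confirming call asks nothing different. Nothing describes collecting burden or depression scores afterwards.

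Solutions, and the visits that deliver them, exist only in the treatment arm. Reluctance that stems from the intervention can therefore arise only there, and it can be taken for reluctance to remain in the study. If such caregivers do differ in outcome from those who stay, the completers in that arm no longer represent the group as randomised. Both primary endpoints (burden and depression) and the 10-month question would be affected.

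The analysis would not repair this. Repeated measures ANOVA in its usual form drops anyone with a missing time point, and ordinary GEE gives no protection when dropout depends on the outcome.

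**Working it through.** **1. The sections side by side.** What is asked on the call is the wish to leave the study (23.4). What is confirmed is that same wish (18.2 and 23.4). What is described as kept is data up to withdrawal (18.3). An option to stop the intervention and continue assessments appears in none of them. The calls have two stated purposes, checking solutions and making appointments. By 16.1 the first applies to the treatment group. The second can apply to both groups, because section 3.0 sets assessments without restriction by arm.

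**2. The plan's own sample size.** Inputs from 16.2: d = 0.65, one-sided alpha 0.05, power 80%.

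n per group = 2(1.645 + 0.842)² / 0.65² = 29.3, rounded up to 30. A noncentral t calculation also gives 30 (power 80.0%). The plan's 30 per group is reproduced.

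With 75 recruited and 25% lost, 75 × 0.75 = 56.25 remain, about 28 per arm. One-sided power is then about 77.5%.

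**3. Is unequal loss a power problem?** Hold total loss at 25% of 75 and split it unequally (treatment/control): 30%/20% gives power of about 77.5%, 35%/15% gives 77.1%, and 40%/10% gives 76.2%. Imbalance alone costs little power, so the issue is bias.

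**4. Illustration of bias.** Let f be the extra fraction lost from the treatment arm and k the amount, in SD, by which those leavers do worse than stayers. Other loss is taken as unrelated to outcome. Neither f nor k is in the documents; both are assumptions.

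Full-arm mean = (1 − f) × stayers + f × leavers, so the completer mean differs from the full-arm mean by f × k, in favour of treatment.

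The one-sided type I error below takes no true effect and 28 completers per arm, with noncentrality f × k × √(28 × 28 / 56).

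| f | k = 0.25 | k = 0.5 | k = 0.8 |
|---|---|---|---|
| 5% | 0.013 SD; 5.5% | 0.025 SD; 6.0% | 0.040 SD; 6.7% |
| 10% | 0.025 SD; 6.0% | 0.050 SD; 7.2% | 0.080 SD; 8.9% |
| 20% | 0.050 SD; 7.2% | 0.100 SD; 10.1% | 0.160 SD; 14.6% |
| 25% | 0.063 SD; 7.9% | 0.125 SD; 11.8% | 0.200 SD; 18.3% |

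Against d = 0.65 the extremes are 0.0125 / 0.65 = 2% and 0.20 / 0.65 = 31%.

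**5. Direction.** The same formula applied to extra loss of worse-off controls gives a shift of f × k against treatment. The sign depends on who leaves, which the documents do not say.

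**The case against.** The call question is a consent safeguard. It is asked only when unwillingness is suspected, it is confirmed by the principal investigator, and it answers a template item on ongoing consent. The unconditional question, at the second and third interviews, covers both arms. Visits vary by case, caregivers help choose the solutions, the intervention lasts only 1–2 months, and the last interview is already by phone, so there is some room to lighten the burden. Section 18.3 says that withdrawal handling is in the consent form, and 23.5 adopts an institutional procedure. Neither was available for this review, so the end of collection at withdrawal is inferred from 18.3 and not stated there.

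These points stand, and they rule out three stronger readings that a reader might infer:

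- That only treated caregivers receive these calls. The appointment purpose, in the same sentence, gives controls a reason to be called too. The protocol does not say whether they are.
- That caregivers are asked to leave when their solutions fail. The stated trigger is suspected unwillingness, and nothing ties it to failed solutions.
- That the results are biased toward benefit by a known amount. Controls who receive only usual support while being interviewed repeatedly may also leave because they are burdened, which would offset or reverse the shift. The plan's 25% attrition is overall, from any cause and not split by arm, so it cannot all be charged to one arm or to one phone question.

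None of this supplies the missing option. A call that confirms only withdrawal does not tell the caregiver that the interviews could continue.

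**Conclusion.** The point holds in a limited form. As written, 23.4 and 18.2–18.3 treat reluctance about the intervention and departure from the study as one event, and no continued assessment is described. Because the solutions and their delivery belong to one arm, loss may differ by arm, and the analysis in 16.1 has no stated means of dealing with it.

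Direction and size cannot be established from the documents. The range of about 0.01–0.20 SD, with one-sided type I error of about 5.5–18% in place of 5%, rests entirely on the assumed 5–25% extra treatment-arm loss, leavers 0.25–0.8 SD worse, other loss unrelated to outcome, and 28 completers per arm. It shows what could be at stake and does not predict it. The change is worth making because it is cheap and because outcomes that were never collected cannot be recovered at analysis.

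**What to change.** Amend 23.4, 18.2 and 18.3 so that stopping the intervention and leaving the study are separate choices:

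- On a call, tell a caregiver who seems unwilling that the visits and solutions can stop while the 2-, 4- and 10-month interviews continue, by phone if preferred. Still state the right to leave entirely.
- Have the principal investigator's confirmation call put the same choice before recording a withdrawal.
- Ask about willingness with the same wording at the same time points in both arms.
- State that caregivers who stop only the intervention stay in their randomised group with all assessments.

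The cost is wording in three sections, one sentence in the consent form and a few more interviews at $20 each. No extra staff are needed, because the confirmation call already exists and the last interview is already by phone.

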24.0 Waiver or Alteration of Consent Process

Consent will not be obtained, required information will not be disclosed, or the research involves deception.

- N/A:** A waiver or alteration of consent is not being requested.

24.1 *If the research involves a waiver or alteration of the consent process, please review the "CHECKLIST: Waiver or Alteration of Consent Process (HRP-410)" to ensure that you have provided sufficient information for the IRB to make the determination that a waiver or alteration can be granted.*

NOTE: For records review studies, the first set of criteria on the "CHECKLIST: Waiver or Alteration of Consent Process (HRP-410)" applies.

Response:

24.2 If the research involves a waiver of the consent process for planned emergency research, please review the “CHECKLIST: Waiver of Consent for Emergency Research (HRP-419)” to ensure you have provided sufficient information for the IRB to make these determinations. Provide any additional information necessary here:

Response:

